#### 6.2.2.2. Tumor Shrinkage

Tumor shrinkage will be summarized as the percent change from baseline in target lesions (sum of longest diameter for non-nodal lesion and short axis for nodal lesion) per time point. It will be derived as:

- $((\text{Sum of target lesions at week XX} - \text{sum of target lesions at baseline}) / \text{sum of target lesions at baseline}) \times 100$ .

The maximum reduction in target lesions from baseline will be derived across all the post-baseline assessments until documented disease progression, excluding assessments after start of subsequent anticancer therapy, as:

- Minimum of  $((\text{sum of target lesions at week XX} - \text{sum of target lesions at baseline}) / \text{sum of target lesions at baseline}) \times 100$ .

A waterfall plot of maximum percent reduction in the sum of longest diameter for non-nodal lesions and short axis for nodal lesions from baseline will be created. This plot will display the best percentage change from baseline in the sum of the diameter of all target lesions for each patient with measurable disease at baseline and at least one adequate post-baseline assessment.

#### 6.2.2.3. Duration of Response (Expansion Cohort Only)

Duration of Response (DR) is defined, for patients with OR, as the time from first documentation of objective response (CR or PR) to the date of first documentation of objective progression of disease (PD) or death due to any cause. If a patient has not had an event (PD or death), DR is censored at the date of last adequate tumor assessment. The censoring rules for DR are as described below for PFS in [Table 3](#).

$$\text{DR (months)} = [\text{date of event or censoring} - \text{first date of OR} + 1] / 30.4375$$

Kaplan-Meier estimates (product-limit estimates) will be presented by treatment group together with a summary of associated statistics including the median DR time with two-sided 95% CIs. In particular, the DR rate at 3, 6 and 12 months will be estimated with corresponding two-sided 95% CIs. The CIs for the median will be calculated according to [Brookmeyer and Crowley](#) and the CIs for the survival function estimates at the time points defined above will be derived using the log-log transformation according to [Kalbfleisch and Prentice](#) (conftype=loglog default option in SAS Proc LIFETEST) with back transformation to a CI on the untransformed scale. The estimate of the standard error will be computed using Greenwood's formula.

DR will be displayed graphically and analyzed using Kaplan-Meier methodology. If the number of patients with OR is small, the Kaplan-Meier method may not provide reliable estimates. In this case, only descriptive statistics or listings will be provided.

#### **6.2.2.4. Time to Response (Expansion Cohort Only)**

Time to response (TTR) is defined, for patients with OR, as the time from the ‘start date’ to the first documentation of objective response (CR or PR) which is subsequently confirmed.

$$\text{TTR (in months)} = [\text{first date of OR} - \text{‘start date’} + 1] / 30.4375$$

TTR will be summarized using simple descriptive statistics (mean, SD, median, min, max, Q1, Q3).

#### **6.2.2.5. Progression-Free Survival (Expansion Cohort Only)**

Progression-Free Survival (PFS) is defined as the time from start date to the date of the first documentation of objective progression of disease (PD) or death due to any cause, whichever occurs first. PFS data will be censored on the date of the last adequate tumor assessment for patients who do not have an event (PD or death), or for patients with an event after two or more missing tumor assessments. For patients who start a new anti-cancer therapy prior to an event, PFS data will be censored on the date of the last adequate tumor assessment prior to starting the new anti-cancer therapy. Patients who do not have an adequate baseline tumor assessment or who do not have an adequate post-baseline tumor assessment will be censored on the ‘start date’ unless death occurred on or before the time of the second planned tumor assessment in which case the death will be considered an event ([Table 3](#)).

In this study antitumor activity will be assessed through radiological tumor assessments conducted at screening, at 9 weeks after the first dose of study drug, and every 6 weeks until disease progression, and at the time of End of Treatment/Withdrawal (if not done in the previous 6 weeks). The allowable time window for disease assessments is  $\pm 7$  days while on treatment and whenever disease progression is suspected (eg, symptomatic deterioration).

The censoring and event date options to be considered for the PFS and DR analysis are presented in [Table 3](#).

$$\text{PFS (months)} = [\text{date of event or censoring} - \text{start date} + 1] / 30.4375$$

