32. **Follow Up:** Patients should be evaluated up to 90 days after last dose of study treatment. Refer to the protocol for specific guidelines. Patients continuing to experience toxicity following discontinuation of study treatment will continue to be followed at least every 4 weeks until resolution or determination, in the clinical judgment of the Investigator, that no further improvement is expected. PK and immunogenicity samples should be collected as described in the PK and Immunogenicity Assessment section in Schedule of Activities ([Table 3](#)). Patients whose disease has not progressed at the end of treatment will enter into disease follow-up. During this follow-up period, patients will have disease assessments performed every 12 weeks \pm 7-days. Once patients have exhibited disease progression or began a new anti-cancer therapy, or 6-month follow-up from the date of the first dose of the last enrolled patient, whichever occurs first, they will be withdrawn from the study. See [Section 4.3.1](#) Contraception for guidelines on contraception checks during this period.
33. **De novo tumor biopsy for biomarker assessment (Dose escalation):** For patients in dose-escalation cohorts, unscheduled optional de novo tumor biopsies may be collected at the discretion of the investigator and sponsor to support the assessment of disease progression.
34. **De novo tumor biopsy for biomarker assessment (Expansion cohorts):** Mandatory for patients in expansion cohorts only. A de novo biopsy will be required at study entry followed by a second biopsy at the time of the Week 9 scans (after 3 cycles of treatment).
35. **Continued Treatment Beyond Cycle 8:** This will be on a reduced visit schedule (Day 1 of each cycle), or as clinically indicated.
36. **Thyroid Function Tests:** To be collected every 2 cycles for the first 8 cycles, and then every 4 cycles (Cycles 1, 3, 5, 7, 11, 15 etc.).
37. **Hepatitis B and C Tests:** Conduct tests for hepatitis B surface antigen, core antibody, and anti-hepatitis C. Other tests may be conducted per standard practice to confirm an active hepatitis infection.

Table 4. Required Laboratory Tests

SAFETY LABORATORY REQUIREMENTS	
Refer to the Schedule of Activities table for specific timepoints and instructions	
Assessments	
Hematology Panel:	Chemistry Panel:
Absolute Neutrophil Count	Sodium
Hemoglobin	Potassium
	Total Calcium
Platelet Count	Creatinine
WBC with differential (5-part if available)	Albumin

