## 2. INTRODUCTION

This SAP provides the detailed methodology for summary and statistical analyses of the data collected in study B1641003. This document may modify the plans outlined in the protocol; however, any major modifications of the primary endpoint definition or its analysis will also be reflected in a protocol amendment.

Statistical analyses will be performed using cleaned eCRF data as well as non-CRF data (ie, biomarker data, PK data). The primary analysis will include all data up to a clinical cut-off date corresponding to 24 months (104 weeks) after the last patient receive the first dose of the study drug. The final analysis of the data will be performed after last patient last visit (LPLV).

Additional analyses of the data may be performed for publication or regulatory reporting purposes.

Throughout this document ‘start date’ refers to first dose of study treatment.

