**Table 3. Outcome and Event Dates for PFS and DR Analyses**

Scenario	Date of event/censoring	Outcome
No adequate baseline assessment	'Start date' a	Censored a
PD or death 
 
- After at most one missing or inadequate post-baseline tumor assessment, OR
 
- <math>\leq 15</math> weeks after 'start date'
 
	Date of PD or death	Event
PD or death after 2 or more missing or inadequate post-baseline tumor assessments	Date of last adequate tumor assessment b documenting no PD before new anti-cancer therapy is given or missed tumor assessments	Censored
No PD and no death	Date of last adequate tumor assessment b documenting no PD before new anti-cancer therapy is given or missed tumor assessments	Censored
Treatment discontinuation due to 'Disease progression' without documented progression	Not applicable	Information is ignored. Outcome is derived based on documented progression only.
New anti-cancer therapy given	Date of last adequate tumor assessment b documenting no PD before new anti-cancer therapy is given or missed tumor assessments	Censored

a However if the patient dies  $\leq 15$  weeks after 'start date' the death is an event with date on death date.

b If there are no adequate post-baseline assessments prior to the PD or death, then the time without adequate assessment should be measured from the 'start date'; if the criteria were met the censoring will be on the 'start date.'

Kaplan-Meier estimates (product-limit estimates) will be presented by treatment group together with a summary of associated statistics including the median PFS time with two-sided 95% CIs. In particular, the PFS rate at 3, 6, 9, 12 and 15 months will be estimated with corresponding two-sided 95% CIs. The CIs for the median will be calculated according to [Brookmeyer and Crowley](#) and the CIs for the survival function estimates at the time points defined above will be derived using the log-log transformation according to [Kalbfleisch and Prentice](#) (conftype=loglog default option in SAS Proc LIFETEST) with back transformation to a CI on the untransformed scale. The estimate of the standard error will be computed using Greenwood's formula.

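### PFS and DR censoring is written for 6-weekly scans until progression, but the protocol scans off-treatment patients every 12 weeks, so one missed follow-up scan can turn a documented progression into a censored time

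*SAP*

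**What the plan says.** - **Schedule in the SAP.** Section 6.2.2.5 gives one schedule for PFS: "at 9 weeks after the first dose of study drug, and every 6 weeks until disease progression". No other schedule appears for the period after treatment ends.
- **Censoring rule.** The text of 6.2.2.5 censors at the last adequate scan "for patients with an event after two or more missing tumor assessments". Table 3 applies this to "PD or death after 2 or more missing or inadequate post-baseline tumor assessments" and counts the outcome as an event if at most one is missing. SAP 6.2.2.3 uses the same rules for DR.
- **Schedule in the protocol.** Under footnote 32 of the Schedule of Activities and Section 6.2, once treatment has ended without PD, "patients will have disease assessments performed every 12 weeks", with a window of ±7 days. The end-of-treatment (EOT) scan is waived if one was done in the preceding 6 weeks.
- **End of follow-up.** Footnote 32 withdraws these patients at PD, at new therapy, "or 6-month follow-up from the date of the first dose of the last enrolled patient", whichever is first. Section 6.2 lists only PD and new therapy. SAP Section 2 sets the primary analysis at a "clinical cut-off date corresponding to 24 months (104 weeks) after the last patient receive the first dose".
- **Landmarks.** PFS rates are planned at 3, 6, 9, 12 and 15 months and DR rates at 3, 6 and 12 months.

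**The concern.** A rule that counts missing scans needs the right list of planned scans. The SAP puts a 6-weekly schedule next to the rule, yet patients in disease follow-up are scanned half as often. A programmer who follows the SAP literally starts each follow-up interval with one scan already missing, so a single lapse does what the rule reserves for two.

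The patients exposed carry much of the long-term information. They include those who stop for toxicity and those allowed to stop after a confirmed complete response (Protocol 5.3.3), so DR is affected directly. Dropping an observed PD and censoring the patient at the earlier scan tends to raise the Kaplan-Meier curve, because the censoring is applied to patients known to have progressed.

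The second matter is when follow-up ends. Two protocol passages disagree, and the answer decides how much off-treatment follow-up supports the later landmarks.

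**Working it through.** **1. Which schedule Table 3 uses.** The early-death exception covers death "unless death occurred on or before the time of the second planned tumor assessment", which Table 3 gives as 15 weeks. First scan at week 9 plus 6 weeks = 15, which agrees. Table 3 is therefore built on the 9-then-6-weekly schedule.

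**2. Counting empty slots.** Take a last adequate scan at T and PD seen g weeks later. A planned slot at T+d is missing if d < g − 1, which allows the 1-week window.

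| Gap g (weeks) | Missing, 6-week count | Missing, 12-week count |
|---|---|---|
| 11 to 13 | 1: event | 0: event |
| 14 to 19 | 2: censored | 1: event |
| 23 to 25 | 3: censored | 1: event |

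- An on-time 12-week scan loses one 6-week slot, so its PD remains an event.
- One missed or non-evaluable follow-up scan gives a gap of 24 weeks. Slots T+6, T+12 and T+18 are empty and the PD is censored at T. On the 12-week schedule only T+12 is missing and the PD counts.

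**3. The switch to follow-up.** If the last on-treatment scan is s weeks before EOT (0 to 6, since the EOT scan is then waived) and the 12 weeks run from EOT, the first gap is 12 + s ± 1, that is 11 to 19 weeks. Gaps over 13 weeks lose two slots, so a fully compliant patient can be censored. The documents do not say what the 12 weeks run from. Later, an early scan followed by a late one, both in window, can be up to 14 weeks apart, with the same result.

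**4. Size.** The documents give no miss rate, time to PD or number of off-treatment patients. A simulation of off-treatment PDs (50,000 patients per setting) assumed exponential time to PD with median 3, 6 or 12 months after EOT, s uniform on 0 to 6 weeks, and scan timing uniform within ±1 week. Ranges are across the three medians; the last column also spans both starting points.

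| Miss rate (assumed) | Censored, 6-week count, 12 weeks from EOT | Censored, 6-week count, 12 weeks from last scan | Censored, 12-week count |
|---|---|---|---|
| 0% | 24–47% | 9–13% | 0% |
| 10% | 39–56% | 23–28% | 3–8% |
| 20% | 51–65% | 35–42% | 9–18% |

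If the 6-week rule is read leniently, as censoring only gaps over 14 weeks, the 0% row becomes 10–31% and 0%.

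**5. Landmarks if the 6-month limit applies.** An off-treatment patient who started x months before the last enrolled patient can be followed to x + 6 months, so reaching 9, 12 or 15 months needs x of at least 3, 6 or 9. With uniform accrual over A months (assumed), the share of off-treatment patients with enough potential follow-up for landmark L is (A − (L − 6))/A, floored at zero:

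| A (months) | 9 months | 12 months | 15 months |
|---|---|---|---|
| 6 | 50% | 0% | 0% |
| 12 | 75% | 50% | 25% |
| 18 | 83% | 67% | 50% |

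Patients on treatment are scanned 6-weekly for up to 32 × 3 = 96 weeks, with the last scan at week 93 (93 × 7/30.4375 = 21.4 months). The 15-month landmark is week 65 (15 × 30.4375/7 = 65.2). A 12-month DR after a week-9 response falls at 9 × 7/30.4375 + 12 = 14.1 months. Both lie within the treatment period.

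**The case against.** Table 3 names no counting grid, and a scan that was never planned is not naturally missing. On that reading the protocol's 12-week schedule governs and one lapse counts as one. The SAP sentence beginning "The allowable time window for disease assessments is" ties its ±7 days to the time on treatment and to suspected progression, so the whole paragraph may be meant for patients on treatment. This reading is possible. It still conflicts with a schedule that the SAP states as running until progression, and two programmers could reach different event counts from the same data.

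It is also fair that the effect would be visible and limited. SAP Table 4 tabulates events lost after missing assessments, each patient's censoring reason is listed, and planned and actual scan days are plotted. No hypothesis is tested (SAP 5.1.1), and with few responders DR falls back to descriptive statistics or listings. These points lower the severity. They do not settle how the rule should be derived.

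Three stronger readings are tempting and not supported:

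- *That off-treatment events are censored as a matter of course.* An on-time 12-week scan leaves the event intact.
- *That the late landmarks cannot be observed.* Patients on treatment and off-treatment patients enrolled earlier can reach them, and Kaplan-Meier allows for staggered follow-up.
- *That the 24-month cut-off contradicts the 6-month limit.* One is a data cut-off for analysis and the other a withdrawal rule for patients in follow-up, so both can operate. The direct contradiction is between footnote 32 and Protocol 6.2.

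**Conclusion.** The concern holds as a moderate one. The SAP states a scan schedule that is wrong for patients in follow-up and places it beside a censoring rule that depends on it. On the SAP's grid, one missed or non-evaluable follow-up scan, or a gap over about 13 weeks at the switch, censors a documented PD that the 12-week schedule would count.

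The slot counts are exact under the stated window convention. The percentages are illustrative. They rest on assumed miss rates, times to PD and scan timing, and apply only to off-treatment PDs. The number of such patients is unknown, since the expansion size is not fixed (Protocol 9.3, SAP 5.1.1). The upward direction of the bias is reasoned, not estimated.

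If the 6-month limit stands, follow-up of late-enrolled, off-treatment patients ends before the later landmarks. This reduces the numbers at risk but does not invalidate the landmarks. PFS and DR are descriptive, secondary, expansion-only endpoints, and the DLT/MTD analysis is unaffected.

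**What to change.** 1. **SAP 6.2.2.5:** describe both schedules, 6-weekly on treatment (after week 9) and 12-weekly in follow-up, each with its ±7-day window.
2. **SAP Table 3:** define a missing assessment against the schedule in force, for PFS and DR alike. State what the first 12-week interval runs from (last scan or EOT) and which interval applies at the switch.
3. **Protocol footnote 32 and Section 6.2:** reconcile them to one end of follow-up, then check it against the cut-off in SAP Section 2.
4. **Reporting:** keep all planned PFS and DR landmarks and show the number at risk at each.

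Items 1, 2 and 4 cost SAP wording and a derivation change, with no extra scans. They should be settled before the data are analysed, so that the choice of rule cannot depend on the results. Item 3 needs a protocol clarification. If the reconciled follow-up runs past 6 months, some off-treatment patients continue 12-weekly scans.

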**Table 3. Outcome and Event Dates for PFS and DR Analyses**

Scenario	Date of event/censoring	Outcome
No adequate baseline assessment	'Start date' a	Censored a
PD or death 
 
- After at most one missing or inadequate post-baseline tumor assessment, OR
 
- <math>\leq 15</math> weeks after 'start date'
 
	Date of PD or death	Event
PD or death after 2 or more missing or inadequate post-baseline tumor assessments	Date of last adequate tumor assessment b documenting no PD before new anti-cancer therapy is given or missed tumor assessments	Censored
No PD and no death	Date of last adequate tumor assessment b documenting no PD before new anti-cancer therapy is given or missed tumor assessments	Censored
Treatment discontinuation due to 'Disease progression' without documented progression	Not applicable	Information is ignored. Outcome is derived based on documented progression only.
New anti-cancer therapy given	Date of last adequate tumor assessment b documenting no PD before new anti-cancer therapy is given or missed tumor assessments	Censored

a However if the patient dies  $\leq 15$  weeks after 'start date' the death is an event with date on death date.

b If there are no adequate post-baseline assessments prior to the PD or death, then the time without adequate assessment should be measured from the 'start date'; if the criteria were met the censoring will be on the 'start date.'

Kaplan-Meier estimates (product-limit estimates) will be presented by treatment group together with a summary of associated statistics including the median PFS time with two-sided 95% CIs. In particular, the PFS rate at 3, 6, 9, 12 and 15 months will be estimated with corresponding two-sided 95% CIs. The CIs for the median will be calculated according to [Brookmeyer and Crowley](#) and the CIs for the survival function estimates at the time points defined above will be derived using the log-log transformation according to [Kalbfleisch and Prentice](#) (conftype=loglog default option in SAS Proc LIFETEST) with back transformation to a CI on the untransformed scale. The estimate of the standard error will be computed using Greenwood's formula.

Frequency (number and percentage) of patients with each event type (PD or death) and censoring reasons will be presented by treatment group. Reasons for censoring will be summarized according to the categories in [Table 4](#) following the hierarchy shown.

**Table 4. PFS Censoring Reasons and Hierarchy**

Hierarchy	Condition	Censoring Reason
1	No adequate baseline assessment	No adequate baseline assessment
2	Start of new anti-cancer therapy before event.	Start of new anti-cancer therapy
3	Event after 2 or more missing or inadequate post-baseline tumor assessments/'start date'	Event after missing assessments a
4	No event and End of study (EOS) = Subject refused further follow-up	Withdrawal of consent
5	No event and lost to follow-up in any disposition page	Lost to follow-up
6	No event and EOS present and no adequate post-baseline tumor assessment	No adequate post-baseline tumor assessment
7	No event and none of the conditions in the prior hierarchy are met	Ongoing without an event

a 2 or more missing or inadequate post-baseline tumor assessments.

The PFS time or censoring time and the reasons for censoring will also be presented in a patient listing.

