6.3. Patient Withdrawal

Patients may withdraw from treatment at any time at their own request, or they may be withdrawn at the discretion of the investigator or sponsor for safety or behavioral reasons, or the inability of the patient to comply with the protocol-required schedule of study visits or procedures at a given study site.

Reasons for discontinuation of study treatment may include:

- Confirmed objective disease progression according to RECIST version 1.1 (see the Study Design [Section 3](#) for details and exceptions);
- Global deterioration of health status requiring discontinuation;
- Unacceptable toxicity (possibly associated with both study drugs);
- Pregnancy;
- Significant protocol violation;
- Lost to follow-up;
- Patient refused further treatment;
- Study terminated by Sponsor;
- Death.

Reasons for withdrawal from study follow-up may include:

- Completed study follow-up;
- Study terminated by Sponsor;
- Lost to follow-up;
- Death.

If a patient does not return for a scheduled visit, every effort should be made to contact the patient. All attempts to contact the patient and information received during contact attempts must be documented in the patient's medical record. In any circumstance, every effort should be made to document patient outcome, if possible. The investigator should inquire about the reason for withdrawal, request the patient to return for a final visit, if applicable, and follow-up with the patient regarding any unresolved AEs.

If the patient refuses further visits, no further study specific evaluations should be performed, and no additional data should be collected. The sponsor may retain and continue to use any data collected before such withdrawal of consent.

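### The last row of the PFS censoring-reason table (SAP Table 4) does not require that the patient is still on study, so some patients who have left are reported as ongoing

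*SAP*

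**What the plan says.** SAP 6.2.2.5 (PFS, expansion cohorts only) tabulates censoring reasons by treatment group using the ordered categories of Table 4, and repeats each patient's reason in a listing. Rows 1 to 3 cover an inadequate baseline, new anti-cancer therapy before an event, and an event after two or more missing or inadequate assessments. The remaining rows concern patients without an event:

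- Row 4: "No event and End of study (EOS) = Subject refused further follow-up".
- Row 5: "No event and lost to follow-up in any disposition page".
- Row 6: "No event and EOS present and no adequate post-baseline tumor assessment".
- Row 7: "No event and none of the conditions in the prior hierarchy are met", labelled "Ongoing without an event".

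The protocol provides other ways to leave the study without an event. Section 6.3 lists completion of follow-up and termination by the sponsor among the reasons for leaving study follow-up. Footnote 32 of the Schedule of Activities adds a time limit for patients in disease follow-up, "6-month follow-up from the date of the first dose of the last enrolled patient", after which they are withdrawn.

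SAP Section 2 sets the primary cut-off at 104 weeks after the last patient's first dose and places the final analysis after the last patient's last visit.

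**The concern.** Row 7 is a residual category with a specific label. A residual row collects whatever the earlier rows miss, so its label is true only if those rows capture every patient who has left. They do not. Row 6 tests for an end-of-study record, but only in combination with the absence of an adequate post-baseline scan. A patient who was scanned and then left for a reason not named in rows 4 or 5 passes through to row 7 and is counted as still under observation.

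A reader uses this table to see why follow-up for PFS stopped. If patients whose observation is closed are mixed with patients still being followed, the table overstates how many can still contribute events. It also has no way to say that a patient is off study without an event.

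**Working it through.** The plan gives no figure to reproduce; the check is of a classification rule.

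**Step 1. Apply Table 4 in order.** Take an event-free patient with an adequate baseline and no new anti-cancer therapy, so that rows 1 to 3 do not apply. Vary the end-of-study (EOS) status and whether there is an adequate post-baseline scan.

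| EOS status | With adequate scan | Without adequate scan |
|---|---|---|
| No EOS record | row 7, label true | row 7, label true |
| Refused further follow-up | row 4 | row 4 |
| Lost to follow-up | row 5 | row 5 |
| Finished follow-up, or footnote 32 limit reached | row 7, label false | row 6 |
| Sponsor ended the study | row 7, label false | row 6 |
| Any other recorded reason | row 7, label false | row 6 |

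Three of the six cells that reach or could reach row 7 with an EOS record do reach it, all in the column with an adequate scan.

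**Step 2. Final analysis.** This follows the last patient's last visit, so the true number ongoing is 0. Row 7 can still be reached when every patient has an EOS record (the three cells marked false). If r patients fall in row 7 among N in a treatment group, the table shows r/N ongoing where the truth is 0/N. All r entries are wrong.

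**Step 3. Primary cut-off, 104 weeks (24 months) after the last patient's first dose.**

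- Footnote 32 limit: 24 − 6 = 18 months before the cut-off. Under that footnote, event-free patients in disease follow-up at that time have already been withdrawn, yet those with an adequate scan go to row 7.
- Planned treatment: 32 cycles × 3 weeks = 96 weeks, which is 104 − 96 = 8 weeks before the cut-off for the last patient enrolled if there are no delays.
- Some patients may truly be ongoing. Cycle 32 is dosed 31 × 3 = 93 weeks after first dose, and footnote 32 evaluates patients up to 90 days after the last dose: 93 + 90/7 = 105.9 weeks, just past the cut-off. Dose delays and agreed continuation beyond 32 cycles (Protocol 5.3.3) extend this further. Protocol 6.2 describes the same disease follow-up without the six-month limit.

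At this cut-off, therefore, between none and all of the row 7 entries may be false; the documents do not fix how many.

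**Step 4. Effect on estimates.** PFS event and censoring dates come from SAP Table 3. Table 4 only names the reason. The Kaplan-Meier curve, the median and the landmark rates are the same whatever row 7 says.

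**The case against.** The strongest reply is that this is one label in a descriptive table for a secondary endpoint, in a study that plans no hypothesis test, and that other outputs show the same facts. SAP 6.5.2.1 tabulates discontinuation of each study drug, and of safety follow-up, by main reason. SAP 6.2.2.5 also plans a comparison of planned and actual assessment days and a reverse Kaplan-Meier plot of follow-up. This stands, and it limits the severity. It does not make the row true: none of these outputs is the tabulation of PFS censoring reasons, and the patient listing would carry the same wrong label.

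A reader might infer something stronger: that row 7 hides patients who left because they were getting worse, so that informative censoring is presented as administrative. The documents do not support this as a general claim.

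- Protocol 6.3 gives "Global deterioration of health status requiring discontinuation" as a reason to stop treatment; it is not on the separate list of reasons to leave follow-up.
- Under Protocol 6.2, patients without progression at the end of treatment go on to disease follow-up. While that lasts, calling them ongoing is correct.
- If such a patient later dies, starts new therapy, refuses or is lost, the patient counts as an event or falls in an earlier row. If the patient has an EOS record and never had an adequate post-baseline scan, row 6 applies.
- The exits that clearly end in row 7 are finished follow-up, sponsor termination and the footnote 32 limit, which are mainly administrative.

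A deteriorating patient can still reach row 7 with a false label, but only once an EOS record exists for a reason other than refusal or loss, after at least one adequate scan.

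**Conclusion.** Wrong as written, minor severity. Row 7 labels as ongoing any event-free patient with an adequate baseline, an adequate post-baseline scan, no new anti-cancer therapy, and an EOS record for a reason other than refusal or loss to follow-up. At the final analysis every row 7 entry would be false, on the assumption that all patients have an EOS record by the last patient's last visit. At the primary cut-off some entries may be false. The number affected cannot be given, because the size of the expansion cohorts is left open (Protocol 9.3, SAP 5.1.1) and no exit rates are stated.

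The consequence is limited to the expansion-cohort PFS censoring-reason table and listing. It would go too far to conclude that the PFS estimates are biased, since Table 3 sets the dates, or that readers have no other view of why patients stopped.

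**What to change.** In SAP Table 4:

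- Restrict row 7 to: *No event and no end-of-study record at the cut-off*. Its label can stay.
- Insert before it: *No event, end of study present, at least one adequate post-baseline assessment*, with the reason *Off study without an event*, split by end-of-study reason (finished follow-up, including the footnote 32 limit; study ended by the sponsor; other).

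The cost is a wording change and a small programming edit. Row 6 already tests for an EOS record, so the derivation has that variable, and the disposition pages supply the reason. No estimate changes. A separate count of treatment stopped for deterioration is not needed here, since the disposition tables already give reasons for stopping each drug. Nor does the fix call for a matching table for duration of response, because the SAP plans the Table 4 summary for PFS only.
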